4.4.5.3 Implant Procedures

Note: The design of the VTAAA stent graft system is modular in nature and allows for bailouts and staging of the procedure following the deployment of each device. The procedure can be stopped at the completion of deployment of each component of the system and the patient has the opportunity for alternate endovascular, open repair techniques, or completion of the procedure at a later date if such conditions arise.

- A. The implantation of the VTAAA stent graft system is conducted under fluoroscopic/angiographic guidance. Refer to the VTAAA stent graft system Instructions for Use (IFU) for techniques and methods for device deployment and implantation.
- B. The VTAAA stent graft system may be implanted in a staged procedure per physician discretion (in either a planned or bail-out fashion). The physician may choose to perform the procedure in two or more stages due to the following conditions/scenarios including but not limited to: hypogastric patency, LSA patency, visceral vessel patency, decreased MEP/SEP potentials, at risk dominant segmental arteries, pulmonary status, or any patient whose physiologic limitations places them at risk because of the expected length of surgery. The preferred method for planned staging is to create a controlled endoleak which provides limited and temporary perfusion to the aneurysm sac. These methods include but are not limited to placing a bare metal stent in the celiac artery bridge, placing a bare metal stent in the bridge to an alternate visceral artery (ie: SMA or renal), or not completing distal seal in the aorta or iliac arteries.
 - a. Thoracic Graft Placement
 - i. This refers to implanting stent-grafts into the thoracic aorta prior to enrollment into the IDE clinical study.
 - ii. Device Visualization and Preparation
Refer to the Instructions for use provided for the thoracic components to be used.

iii. Device Placement

Ensure that the distal edge of the thoracic graft is 5-7 cm proximal to the celiac artery.

iv. Thoracic Aorta Component Deployment

Follow the study protocol or IFU for deploying the thoracic graft components.

v. Completion

The date of the index procedure will be targeted for within 6 weeks of the thoracic graft placement, but will be based on physician discretion, clinical presentation, and patient compliance.

b. Planned Staged Procedure: Visceral artery bridge endoleak

i. This refers to leaving open a portion of the covered stent bridge between the visceral manifold and target vessel. This is achieved by combining bare metal stents with covered stents to leave ~1-2cm of uncovered conduit along the pathway. This intentional endoleak is resolved in a subsequent intervention where the open portion is covered over by an additional covered stent. It is preferable to achieve this configuration with the bridge to the celiac artery but it can be done in analogous fashion with either the SMA or renal arteries.

ii. Device Visualization and Preparation

Refer to the Instructions for use provided for the bare metal stent for visualization and preparation instruction.

iii. Bridging Stent Deployment

Follow directions in the IFU when deploying bridging stents. Always deploy a covered stent in the leg of the visceral manifold per the VTAAA stent graft

system IFU. When possible, covered stents should be used in the target vessel. The chain of covered stents should be non-continuous in nature with at least one bare metal balloon expandable stent connecting them. The segment of completely bare stent should be short (~1-2cm) with 2-3cm overlapping with covered stent on either side. Creation of the uncovered segment in as straight of configuration as the anatomy allows will facilitate wire passage during the completion procedure below.

Note: The controlled endoleak should never be created by leaving a visceral manifold limb unconnected to a visceral vessel or with an uncovered segment >2cm due to the pressurization of the aneurysm sac. If a visceral vessel is occluded, the corresponding visceral manifold limb should be plugged with a vascular plug and an alternative (patent) vessel utilized for the staging procedure. The placement of the non-continuous chain of covered bringing stents and a bare metal stent helps direct flow while creating a controlled endoleak.

iv. Completion

Completion of the staged procedure is targeted for 4-6 weeks following the index procedure, but will be based on physician discretion, clinical presentation, and patient compliance.

Note: The physician may choose to complete the procedure earlier if the patient is symptomatic or has other concerns for aneurysm sac growth or rupture.

Completion procedure may be performed under local or general anesthesia. Vascular access will be established in the brachial or axillary artery. The staged

limb of the visceral manifold will be cannulated, and the bare segment will be covered over by at least one iCAST or VBX.

c. Planned Stage Procedure: Delayed distal seal

i. This refers to completing the visceral debranching (manifold to target arteries) with covered stents and subsequently leaving out one or more of the distal aortic/iliac components.

ii. Device Visualization and Preparation

Refer to the Instructions for use provided for the distal aortic/iliac components to be used.

iii. Distal Aortic/Iliac Component Deployment

Follow the study protocol or IFU for deploying the distal aortic/iliac components.

iv. Completion

Completion of the staged procedure is targeted for 4-6 weeks following the index procedure, but will be based on physician discretion, clinical presentation, and patient compliance.

Note: The physician may choose to complete the procedure earlier if the patient is symptomatic or has other concerns for aneurysm sac growth or rupture.

Completion procedure may be performed under local or general anesthesia.

d. Bail-out Stage Procedure

i. A bail-out method may be used for staging in the event patient status declines during the case or inability to technically complete the case.

ii. Device Visualization and Preparation

Refer to the Instructions for use provided for the components to be used.

iii. Device Deployment

Refer to the Valiant Thoracoabdominal Stent Graft System (IFU) for device deployment and implantation of the remaining components.

iv. Completion due to patient status decline

Completion of a bail-out staged procedure due to patient status should be completed as soon as clinically feasible following the index procedure, but will be based on physician discretion, clinical presentation, and patient compliance.

Note: The physician may choose to delay staging if the patient has complications or there are concerns with completing the secondary procedure.

v. Completion due to inability to technically complete the case

Completion of a bail-out procedure due to technical challenges have the following options that present no more risk than the alternative of no treatment.

- a. Complete case at another date
- b. Medical management
- c. Convert to open surgical repair
- d. Referral to another facility/investigator that can complete the procedure

C.

- *Note: If treating a dissected aorta, naturally occurring fenestrations will be utilized first, and if necessary, there may be the additional use of an excimer laser or perforating*

needle and catheter to perforate the intimal membrane. This perforation will be used to enter either the false or true lumen in order to accommodate placement of the device.

- *Note: Caution should be taken when relining previously placed graft material to prevent complications from graft on graft friction including decreased graft maneuverability and challenges repositioning.*
- *Note: For proximal extension of the thoracic bifurcation, two Valiant Captivia or Valiant Navion thoracic grafts can be used. One to extend the landing zone more proximally and one to layer to prevent wear. Deploy the Valiant Captiva or Valiant Navion thoracic grafts according to their respective manufacturer's IFU and continue according to the VTAAA stent graft system IFU.*
- *Note: For type 1 and 5 aneurysms the distal end of visceral bypass (VB) should be sized to provide the distal seal with the aorta and then proceed to Step 4.4.5.5, Completion Procedures.*
- *Note: If the VB is too short or too small to provide distal seal, a Valiant Captivia stent graft or Endurant Limb may be used in place or in conjunction with the Visceral Bypass to provide adequate distal seal. For type 2 and 3 proceed to deployment of the infrarenal bifurcation and Endurant II limb stent graft instructions in the VTAAA stent graft system IFU. If a commercially available Endurant limb or Valiant stent graft is used as the Visceral Bypass a commercially available Endurant mainbody stent graft with suprarenal fixation and a Gore cuff is required for adequate fixation. See Step 1.4.5.5.3.C and Step 1.4.5.5.4.D. below for deployment procedures.*
- *Note: if treating a subject with an occluded visceral vessel, a vascular plug may be used to occlude the extra limb of the Visceral Manifold stent graft.*

B. Surgical Decision Pathway and Bailouts

[figure not shown]

Figure 4: Surgical decision path and possible bailouts

C. Visceral Bypass (VB) Instructions (Endurant Long Limb)

1. Insert a guidewire from the groin through the 16-mm limb of the thoracic bifurcation.
2. Refer to the manufacturer's IFU (Endurant) for visualization and preparation instructions.
3. The proximal radiopaque marker of the VB stent graft should be aligned with the bifurcation of the thoracic bifurcation.

4. Verify there is a 5 cm overlap with the 16 mm leg of the thoracic bifurcation.
5. Deploy the VB according to the manufacturer's IFU (Endurant).
6. Leave the guidewire in place and remove the delivery system according the to manufacturer's IFU (Endurant).

D. Infrarenal Bifurcation (IB) Instructions (Endurant Mainbody)

1. Refer to the manufacturer's IFU (Endurant) for visualization and preparation instructions.
2. Identify the guidewire that passes through the VB stent graft.
3. From the ipsilateral groin access point, insert the delivery system over the guidewire.
4. Slowly advance the bifurcated graft into the VB stent graft.
5. Verify there is a 4-5cm overlap with the VB stent graft.
6. Confirm the distal portion of the contralateral leg is above the aortic bifurcation.
7. Confirm the radiopaque ring marker on the distal end of the contralateral leg is in a position to allow for cannulation from the contralateral iliac artery.
8. Confirm the distal target landing zone relative to anatomical landmarks (i.e. internal iliac artery).
9. Deploy the bifurcated graft according to the manufacturer's IFU (Endurant).
10. Release the tip capture mechanism according to the manufacturer's IFU (Endurant).
11. Remove the delivery system according the to manufacturer's IFU (Endurant).

12. Complete distal seal of the bifurcated graft into the common iliacs according to the manufacturer's IFU (Endurant).
13. If the Endurant mainbody with suprarenal fixation is used deploy a Gore Aortic Extender Endoprosthesis according to the manufacturer's IFU (Gore Excluder) over the suprarenal fixation stent of the bifurcated graft (Endurant mainbody) to seal and prevent endoleaks in the event the suprarenal fixation stent were to puncture the graft material.

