3.3.3.9 Staged Endovascular Repair

3.3.3.9.1 Planned Staged Procedures

Staged procedures have been used in endovascular repair of thoracoabdominal aortic aneurysms in an effort to limit the incident and severity of spinal cord ischemia. The hypothesis behind this is the staging of procedures allows for the development of a collateral network. The collaterals would maintain some perfusion and allow other vessels to compensate reducing the overall impact of spinal cord ischemia. One center studying 87 Type II subjects found that staging reduced the overall SCI rates significantly⁶⁶. The SCI rate in single stage procedures was 37.5% (12/32) and 11% (3/27) in two-stage procedures. The rate was slightly higher in unintentionally staged procedures at 14% (4/28). Unintentional staging was defined as prior aortic repair, 21% (6/28) had prior thoracic repair and the remainder were abdominal aortic repair. In the staged procedures, the two-stage repair SCI events were all temporary and resolved by discharge and the unintentional staging had 10% (3/28) that resulted in permanent SCI. This study had a median time between stages of 5 months (range 1-60 months), but the investigators believe 2-3 weeks to be optimum⁶⁶. The investigators also noted that symptomatic patients should be monitored and considered for earlier repair. While there is no specific length of aortic coverage to determine the threshold where one should consider staging, this study cites that aortic coverage of 200 cm or greater may indicate the threshold where subjects would benefit from staging.

There are several techniques used for staging endovascular TAAA repair. Techniques include coverage of the proximal thoracic aorta up to the celiac artery in a staged procedure with visceral

stenting performed at the completion procedure. Other techniques reference placing the main aortic stents, but allowing perfusion from an open celiac branch, perfusion branches, or unstented contralateral iliac limb⁶⁷. The use of perfusion branches may be preferred to allow for better hemodynamics and avoid excessive pressurization of the aneurysm sac.

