3.4.2.1 Staged Procedures

With the Valiant Thoracoabdominal Stent Graft System, the risks of planned staging via the visceral artery bridge endoleak are comparable to the single stage procedure in the current protocol. We do not believe staging presents any new risks that are not currently covered under the risk profile for the VTAAA system, but these risks may happen at a higher frequency. These risks still present no greater risk than the probable risk from the progression of the patient's condition. The increased risks for a planned stage procedure (visceral artery bridge endoleak or delayed distal seal) are risks from an additional procedure including anesthetic and contrast exposure, compounded physiologic insult from

multiples procedures, access site complications, wire injury, device integrity issues from component interaction, paraplegia, spinal cord ischemic event, aneurysm enlargement, aneurysm rupture, and death. Increased risks for a bail-out staged procedure include the above risks and increased procedure time or failure to treat.

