4.4.3 Study Endpoints

The primary safety endpoint is freedom from major adverse events (MAE) at 30 days or during hospitalization if this exceeds 30 days.

Major adverse events include death, bowel ischemia, myocardial infarction, paraplegia, renal failure, respiratory failure, and stroke.

The primary effectiveness endpoint is the proportion of the study subjects with treatment success at 1 year. Treatment success is defined as a composite of technical success and freedom from the following:

- Aneurysm enlargement i.e., greater than 5mm as compared to any previous CT measure using orthogonal (i.e., perpendicular to the centerline) measurements
- Aneurysm rupture
- Aneurysm-related mortality
- Conversion to open repair
- Secondary intervention for migration, Type I and III endoleaks, device integrity failure (e.g., fracture), and patency-related events (i.e., device component stenosis or occlusion and embolic events)

Secondary endpoints include:

- Technical success and the individual components of technical success:
 - Successful delivery
 - Deployment at the intended implantation site
 - Patency of all endovascular graft and stent components
 - Absence of device deformations requiring unplanned placement of an additional device
 - Absence of inadvertent covering of aortic branch vessels
 - Successful withdrawal

- Freedom from the individual components of the primary safety endpoint at 30 days:
 - Death
 - Bowel ischemia
 - Myocardial infarction
 - Paraplegia
 - Renal failure
 - Respiratory failure
 - Stroke
- Freedom from paraparesis at 30 days
- The following at each follow-up interval:
 - Treatment success and the individual components of treatment success including freedom from the following:
 - Aneurysm enlargement
 - Aneurysm-related mortality
 - Aneurysm rupture
 - Conversion to open repair
 - Secondary intervention for migration, type I and III endoleaks, device integrity failure (i.e., fracture), and patency-related events (i.e., device stenosis or occlusion and embolic events).
 - Renal failure
 - All-cause mortality
 - Endoleaks
 - Device integrity failure (e.g., fracture)

- Patency-related events (i.e., device stenosis or occlusion and embolic events)
- Other device-related events

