The sponsor will report at intervals of every five patients treated in the primary study arm (upon ten days following the 30-day follow-up of the fifth patient). Additionally, the sponsor will report a progress report for each patient treated under the expanded selection arm (upon ten days following the 30-day follow-up). These reports will include the following information:

Basic information on the number of patients enrolled and treated and information on observed adverse events for any subgroups (e.g., device types, extents of disease, lesion

types). These interim progress reports are meant to be summaries and not complete progress reports. Details will be captured in any adverse event reports and annual reports to the IDE.

Table 9: Enrollment summary*

	column for each subgroup	Total
Enrolled		
Treated		
Awaiting treatment		
Withdrawn (state reason)		

* A subject is considered enrolled after the device enters the body.

Summary

For each subgroup of patients, a brief narrative description of the procedures completed to date (e.g., how many had devices implanted successfully), any need for additional interventions, and the outcomes of any additional interventions will be provided.

Table 10: Treatment summary

	Number of patients	Procedural success	Perioperative death
One branch			
Two branches			
Three branches			
Four branches			
Total			

Adverse Events

Comments on the most commonly observed challenges or adverse events will be provided.

The following table is an example of how adverse event numbers may be presented for each subgroup. The list will include events observed in the study, not necessarily all that are listed in this example.

	1 st 5	2 nd 5	Additional groups	All
Aortic dissection				

Branch vessel embolism (renal, celiac, SMA, etc.)				
Branch vessel occlusion (renal, celiac, SMA, etc.)				
Branch vessel dissection (renal, celiac, SMA, etc.)				
External iliac dissection				
Interval iliac occlusion				
Ischemic colitis/Colon necrosis				
Late related death				
Late unrelated death				
Leg ischemia				
Lower extremity embolism				
Lower extremity paralysis				
MI				
Perioperative death				
Renal failure/impairment				
Respiratory failure				
Stroke				
Wound necrosis				

Table 6: Adverse Events

Study subjects who had multiple complications will be designated using symbols (#, *, +) or numbers.

Lessons Learned

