4.9 Definitions

Aortic aneurysm enlargement: ≥ 5 mm as compared to any previous CT measure using orthogonal (i.e., perpendicular to the centerline) measurements

Aortoiliac aneurysm: aneurysm of the abdominal aorta and including one or both of the iliac arteries

Aneurysm-related mortality:

Death occurring within 30 days or during hospitalization following the index procedure, unless there is evidence of accidental or self-inflicted death.

Death occurring within 30 days or during hospitalization following conversion to open repair or a secondary intervention for migration, Type I and III endoleaks, device integrity failure (e.g., fracture), or patency-related events (i.e., device stenosis or occlusion and embolic events), unless there is evidence of accidental or self-inflicted death;

Death occurring within 30 days or during hospitalization for a complication of the aneurysm or a complication associated with the device, such as:

- aortic rupture
- fistula formation (e.g., aorto-enteric)
- embolization
- malperfusion of organ(s) or limb(s)

Arterial fistula formation: formation of an abnormal connection or passageway between an artery and adjacent structures

Crawford Type IV TAAA: aneurysmal dilation originating within 5 cm of the celiac artery.

Conversion to Open, Early: any open repair within 30 days of the index procedure involving the vasculature in the abdomen and/or pelvis.

Conversion to Open, Late: any open surgical repair involving stent graft removal after 30days post index procedure

Chronic Obstructive Pulmonary Disease (COPD): forced expiratory volume (FEV1) < 1.0 liter or receiving home oxygen

Disabling stroke: Modified Rankin Score MRS >2

Distal landing zone: aortic fixation site furthest from the heart

Embolization: dislodging of an upstream particle that travels downstream causing blockage of free flow further downstream. Embolization could result in malperfusion

Embolus: blood clot that forms at one location (presumably from the aneurysmal sac, aortic neck, or adjacent vessels) and is dislodged to another location resulting in ischemic changes

Emergent: an aneurysm requiring immediate treatment

Endoleak:

Type I: leak occurring at the proximal or distal fixation site, including leakage around fenestrations

Type Ia: leak occurring at the proximal fixation zone of the stent-graft

Type Ib: leak occurring at the distal fixation zone of the stent graft

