Type Ic: leak occurring at the distal fixation zone of the covered stents in the visceral vessels incorporated by the fenestrations

Type II: leak caused by retrograde flow from patent lumbar or inferior mesenteric arteries

Type IIIa: leak caused by a defect in the graft fabric

Type IIIb: leak caused by inadequate seal between modular graft components

Type IV: leak caused by graft fabric porosity, often resulting in a generalized blush of contrast within the aneurysm sac

Endoleak, Early: any endoleak observed within 30 days after device deployment

Endoleak, Late: any endoleak observed later than 30 days after deployment that was not documented during the first 30 days after deployment

Estimated Glomerular Filtration Rate (eGFR): estimated GFR (mL/min/1.73 m²) = 175 x (Serum creatinine)^{-1.154} x (Age)^{-0.203} x (0.743 if female) x (1.210 if African American)

Graft Relining: placement of the investigational system that results in landing zones that extend beyond the limits of the previously placed graft material

Limb occlusion: the presence of thrombus within any graft limb that creates occlusion

Major adverse events: all-cause mortality, bowel ischemia (requiring medical or surgical management), myocardial infarction, paraplegia, renal failure, respiratory failure, and stroke

- **All-Cause Mortality:** any death occurring within the first 30 days post procedure

- **Bowel Ischemia:** Bowel ischemia due to limb or arterial occlusion, graft placement, or embolization.
- **Myocardial infarction:** raised levels of cardiac biomarkers or ECG changes
- **Paraplegia:** spinal cord ischemic event resulting in complete loss of motor function with or without loss of sensation in the lower extremities
- **Renal Failure:** acute or progressive renal insufficiency leading to the need for dialysis or hemofiltration
- **Respiratory failure:** prolonged intubation (>48 hours after spinal drain removal or >72 hours total) and/or reintubation. This definition does not put the patient at any increased risk. The high-risk patient population being treated in this study is prone to pre-existing comorbidities, including COPD and decreased respiratory function, and may require extended ventilator support while in the supine position for spinal drainage.
- **Stroke:** neurological deficit that lasts > 24 hours

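### A thoracic graft placed as the first stage of the repair falls before enrolment, so deaths after it cannot be study events and other complications become baseline history

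*Combined protocol and SAP*

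**What the plan says.** Section 4.4.5.3, item B, allows the system to be implanted in stages at the physician's discretion and lists four sub-items: (a) thoracic graft placement, (b) visceral artery bridge endoleak, (c) delayed distal seal and (d) bail-out. Item a is defined as follows: "This refers to implanting stent-grafts into the thoracic aorta prior to enrollment into the IDE clinical study". It still gives a landing position relative to the celiac artery, points to the study protocol or IFU for deployment, and sets a timetable: "The date of the index procedure will be targeted for within 6 weeks of the thoracic graft placement".

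For items b and c the order is reversed: the index procedure comes first, and completion is targeted 4-6 weeks later.

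Other relevant text:

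- Enrolment (section 4.7, footnote to Table 9): "A subject is considered enrolled after the device enters the body".
- Primary safety endpoint (section 4.4.3): "The primary safety endpoint is freedom from major adverse events (MAE) at 30 days or during hospitalization if this exceeds 30 days". It does not say which procedure starts the clock.
- Death as a major adverse event (section 4.9): "any death occurring within the first 30 days post procedure", again without naming the procedure. Aneurysm-related mortality is anchored explicitly: "Death occurring within 30 days or during hospitalization following the index procedure".
- Table 5 runs from pre-op to the index procedure, with extra columns only for a later completion stage.
- The recent-procedure exclusion in section 4.4.2 covers only procedures unrelated to treating the aneurysm.

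**The concern.** An incidental graft in the patient's history would need no landing instruction and no target date for what follows. In substance item a is the first operation of a planned repair, and section 3.3.3.9.1 describes thoracic coverage down to the celiac artery as a recognised staging technique. Placing it before enrolment has three effects.

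1. A patient who dies after the thoracic stage is never in the study, in either numerator or denominator.
2. A patient who survives a stroke, paraplegia or renal failure before enrolment can enter with that event as baseline history. Raised creatinine or two failed organ systems would move the patient from the primary to the expanded arm.
3. Subjects staged by different routes are counted differently. Section 4.4.7 pools data across the parallel PS-IDEs with a split by study arm but none by staging route.

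Death, stroke, paraplegia and renal failure are all components of the primary safety composite, so the observed rate would be selected in the device's favour. Events that were never recorded, and patients who were never logged, cannot be recovered at analysis.

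**Working it through.** **Step 1: which first-stage events count.**

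| Route | First operation | Is it the index procedure? | Table 5 column for it | Events after it |
|---|---|---|---|---|
| a. Thoracic graft | Thoracic graft | No, precedes enrolment | None | Not study events if before enrolment |
| b. Bridge endoleak | VTAAA implant | Yes | Intra-op Index | Count |
| c. Delayed distal seal | VTAAA implant | Yes | Intra-op Index | Count |

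The index anchor for major adverse events (MAEs) is inferred, because sections 4.4.3 and 4.9 do not name it. No reading found in the plan brings pre-enrolment events into the count.

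**Step 2: reproduce the plan's test.** Inputs from section 4.4.7.1: exact method, one-sided 2.5%, goal 50%, anticipated MAE rate 26%, 46 pooled subjects. Let X be the number of MAE-free subjects, binomial with n = 46. The smallest r with P(X ≥ r | 0.50) ≤ 0.025 is r = 31, so the test passes with at most 15 MAEs.

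- Exact type I error: P(X ≥ 31 | 0.50) = 0.0129.
- Power: P(X ≥ 31 | 0.74) = 0.881. The stated power of at least 80% holds.

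**Step 3: effect of uncounted first-stage events.** The documents give neither quantity needed, so both are assumptions:

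- f = share of pooled subjects on route a, taken as 10% to 50%;
- s = probability of an MAE in the thoracic stage, taken as 5% to 20%.

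If first-stage and later events are independent, the whole-repair rate W (thoracic stage plus index) relates to the counted rate c by W = c + f·s·(1 − c), so c = (W − f·s)/(1 − f·s). Set W = 0.50, where the test should rarely pass, and compute P(X ≥ 31 | 1 − c):

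| f | s | f·s | c | False-pass probability |
|---|---|---|---|---|
| 0 | – | 0 | 0.500 | 0.013 |
| 10% | 5% | 0.5% | (0.5 − 0.005)/0.995 = 0.497 | 0.014 |
| 25% | 10% | 2.5% | (0.5 − 0.025)/0.975 = 0.487 | 0.020 |
| 50% | 10% | 5% | (0.5 − 0.05)/0.95 = 0.474 | 0.031 |
| 50% | 20% | 10% | (0.5 − 0.10)/0.90 = 0.444 | 0.070 |

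The nominal 0.025 is crossed when f·s is about 4% (at 3.75% the probability is 0.0247).

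**Step 4: sensitivity at the boundary.** One-sided exact p-values against 50%:

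- 15/46 counted: p = 0.0129, pass.
- One uncounted MAE in an enrolled subject, 16/46: p = 0.0270, fail.
- One omitted first-stage death, added to numerator and denominator, 16/47: p = 0.0200, pass.
- Two such deaths, 17/48: p = 0.0297, fail.

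**The case against.** The best defence is that the study assesses the VTAAA system, and that a thoracic graft deployed under its own instructions is not that system. On this view the primary composite should start when the investigational device is used. That is a fair choice of estimand, and it is why the fix below leaves the index-based rate as primary. It does not justify leaving a directed first stage unrecorded.

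The route may also be uncommon. Items b and c are headed as planned and item a is not. The stated preference is a controlled endoleak, and section 3.4.2.1 confines its staging risks to two routes: "The increased risks for a planned stage procedure (visceral artery bridge endoleak or delayed distal seal". The six staged cases in section 3.5.1 used those same two routes. All of this stands, and it limits the likely size. Section 4.5.1.4 sends subjects at high risk of spinal cord ischemia to a standardized staging protocol, but nothing in the documents says that this protocol uses item a.

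Nor do routes b and c capture everything. Their completion stage, targeted at 28 to 42 days after the index procedure, mostly falls outside a 30-day window that starts at the index procedure.

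A reader might go further in four ways that the documents do not support:

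- **That stroke and paraplegia survivors are never enrolled.** Only death has that certain effect. No exclusion names prior stroke or paraplegia, the expanded arm accepts poor performance status, and a delayed complication first appearing after the index procedure would count.
- **That up to 11 points of paraplegia are missing.** Section 3.3.3.9.1 reports: "The SCI rate in single stage procedures was 37.5% (12/32) and 11% (3/27) in two-stage procedures". Those events are spinal cord ischemia of any degree in Type II patients. In the two-stage group all were temporary, and no split by stage is given. The MAE definition requires complete loss of motor function.
- **That one lost event is worth 12.5 points (1/8).** The hypothesis test is sized on 46 pooled subjects, where one event is 1/46 = 2.2 points, and an omitted death also leaves the denominator.
- **That open repair is charged with every stage while the device is not.** Table 6 gives only event counts and does not show whether those series included staged aortic procedures.

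**Conclusion.** The concern holds as a gap in what is captured. Followed as written, the plan directs a first stage, puts it before enrolment, and yields an MAE rate among those who reach the index procedure. Deaths in the interval cannot be study events, and non-fatal events in it become history.

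The size of the bias is unknown. If the route is rare it is negligible. It pushes the false-pass probability above the nominal 2.5% only once about 4% of all pooled subjects have a first-stage MAE. The range of 0.014 to 0.070 rests on assumed values of f and s, on independence between stages, on an index-based MAE clock, and on the other pooled PS-IDEs treating this stage in the same way. The case for acting rests on low cost, on the impossibility of retrospective repair, and on a pass that can turn on one or two events at the boundary.

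**What to change.** For any thoracic graft placed with a VTAAA repair already planned:

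1. Obtain consent before that stage and log the patient.
2. Add a thoracic-stage column to Table 5.
3. Record MAEs for 30 days (or the hospitalization, if longer) after that stage as well as after the index procedure, and name the procedure that starts each window in sections 4.4.3 and 4.9.
4. Report every logged patient who does not reach the index procedure, with the reason.
5. Report a whole-repair MAE rate (thoracic-stage plus index events, with non-completers in the denominator) beside the index-based primary rate, by staging route in the pooled data.
6. State in the Table 9 enrolment footnote how these logged patients are counted, so that a non-completer need not use one of the 15 places.

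Thoracic grafts placed with no VTAAA repair in view remain medical history.

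The cost is protocol wording, one schedule column, earlier consent and slightly more data collection. No procedure is added and no treatment changes. The whole-repair rate may be less favourable than the index-based one.
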